7.3 Setting

7.3.1 Context and rationale for definition of Time 0 (and other primary time anchors) for entry to the study population

Figure 2 displays the study design diagram for the primary analysis. Candidate exposed and comparator patients will be identified as those initiating treatment for metastatic disease with palbociclib and/or letrozole. Study exposure group will be ascertained within a 15-day time

window (i.e., 'exposure ascertainment window'), beginning on the day of the first record of a study drug (palbociclib or letrozole) (Day -15), and ending 15 days later on Day -1. Patients experiencing an outcome or censoring event during this window will be excluded. Additional information on the exposure ascertainment window is provided in [Section 7.4.1](#). Follow-up for progression and death will begin on Day 0 ('Time 0'). To avoid immortal time bias, Time 0 will occur after the exposure ascertainment window for all patients, irrespective of exposure status. The operational definition of Time 0 is provided in [Table 3](#). The date of first study drug initiation will be restricted to dates from February 1, 2010 to June 20, 2023 to reflect current treatment paradigms at the time of the PALOMA-2 trial, and to allow a minimum available follow-up time of one month prior to the end of data for all patients, respectively. It should be noted that the first line of metastatic treatment can be initiated up to 30 days before the documented date of metastatic diagnosis per the data vendor's line of therapy definitions.

Table 3. Operational definition of Time 0

Study population name(s)	Time Anchor Description	Type of entry	Washout window	Incident with respect to...
Patients initiating first-line treatment for metastatic ER+/HER2- breast cancer	Time 0 will be defined as the day after the end of the 15-day exposure ascertainment window. Exposure ascertainment is described in the variables section of this protocol.	Incident	[Metastatic diagnosis date, Day -16]	Metastatic diagnosis

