
Patients treated within the last 7 days prior to randomization with: Food or drugs that are known to be Cytochrome P450 3A4 (CYP3A4) inhibitors; drugs that are known to be CYP3A4 inducers; drugs that are known to prolong the QT interval
	
Treatment with a CYP3A4 inhibitor or inducer or drugs known to prolong the QT interval, as specified in the PALOMA-2 trial protocol. Consumption of foods known to be CYP3A4 inhibitors (grapefruit, grapefruit juice) and use of St. John's Wort cannot be operationalized.
	
[Day -45, Day -15]
	
To account for real-world frequency of medication capture in the EHR, this exclusion criteria will be assessed in the 30 days prior to study drug initiation. Food consumption and supplement use cannot be identified in the data source.
	
Patients with less recent exposure to these treatments who would have been eligible for the trial may be excluded. Conversely, patients with grapefruit or St. John's Wort exposure who would have been ineligible for the trial may be included. This may affect comparability between the study and trial populations.

Major surgery, chemotherapy, radiotherapy, any investigational agents, or other anti-cancer therapy within 2 weeks before randomization. Patients who received prior radiotherapy to ≥25% of bone marrow are not eligible independent of when it was received
	
First-line regimen for metastatic disease prior to study drug initiation. Anti-cancer therapy other than study treatment in the same first-line therapy or neoadjuvant or adjuvant therapy. Major cancer-related surgery. Radiotherapy to ≥25% of bone marrow cannot be operationalized.
	
[Day -29, Day -16]
	
Non-cancer surgeries cannot be identified in the data source. Extent of radiotherapy cannot be identified in the data source.
	
Patients with recent major non-cancer surgery or radiotherapy to ≥25% of bone marrow who would have been ineligible for the trial may be included. This may affect comparability between the study and trial populations.

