Time interval between initial diagnosis and metastatic diagnosis (approximate disease-free interval)	N/A	Continuous	[Initial diagnosis date, Metastatic diagnosis date]
Prior neoadjuvant or adjuvant chemotherapy	Yes, no	Dichotomous	[Start of data, Day -16]
Prior neoadjuvant or adjuvant hormone therapy	Yes, no	Dichotomous	[Start of data, Day -16]
Surgery in the curative setting	Yes, no	Dichotomous	[Start of data, Day -16]
Radiation in the curative setting	Yes, no	Dichotomous	[Start of data, Day -16]
Recurrence type	Recurrent, de novo metastatic, missing	Categorical	[Initial diagnosis date - 30, Initial diagnosis date + 90]
Metastatic disease site	Visceral (lung, including pleura, liver), non-visceral (all others), bone only	Categorical	[Start of data, Day -15]
Number of metastatic disease sites	1, 2, ≥3	Continuous, Categorical	[Start of data, Day -15]

N/A = not applicable

^a See [Appendix C](#) for code list.

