	
 5. Prior hormonal therapy (yes, no) 6. Performance status (ECOG 0 or Karnofsky Score 100, ECOG 1-2 or Karnofsky Score 50-90) 7. Bone-only disease at baseline (yes, no) 8. Prior chemotherapy (yes, no) 9. Most recent therapy (aromatase inhibitor, antiestrogen) 10. Number of disease sites (1, ≥2)
--	---

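### Table 5's two-week exclusion row does not carry over the trial's bar on recent radiotherapy, and the gap is not disclosed

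*Combined protocol and SAP*

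**What the plan says.** Section 7.3.3 states that the exclusion criteria correspond to those applied in the PALOMA-2 trial. In the relevant row of Table 5, the trial criterion is given as "Major surgery, chemotherapy, radiotherapy, any investigational agents, or other anti-cancer therapy within 2 weeks before randomization". A second clause makes patients ineligible if a large share of their bone marrow was ever irradiated.

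The real-world column replaces this with an earlier first-line regimen for metastatic disease, followed by "Anti-cancer therapy other than study treatment in the same first-line therapy or neoadjuvant or adjuvant therapy. Major cancer-related surgery". The assessment window is [Day -29, Day -16]. The column closes with one statement on radiotherapy: "Radiotherapy to ≥25% of bone marrow cannot be operationalized". The rationale column adds: "Extent of radiotherapy cannot be identified in the data source". The validity column reads: "Patients with recent major non-cancer surgery or radiotherapy to ≥25% of bone marrow who would have been ineligible for the trial may be included".

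Elsewhere, Table 9 (Section 7.4.4) lists "Radiation in the curative setting" as a yes/no covariate. Appendix C gives a list of surgery names for this row and has no radiotherapy entry.

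**The concern.** The trial criterion has two separate radiotherapy clauses. One concerns timing (within two weeks) and the other concerns extent (share of marrow, at any time). The plan deals with the extent clause openly: it says the clause cannot be applied, why, and who may be wrongly included. The timing clause is neither applied by name, nor declared infeasible, nor listed as a limitation.

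What is at stake is who enters the cohort. The plan aims for a trial-similar population and judges success by agreement with the trial in direction and magnitude (Section 5). An eligibility difference that is not recorded makes any disagreement harder to interpret. Radiotherapy shortly before first-line treatment may also mark symptomatic disease. If it is related to treatment choice, the propensity model sees it only through other variables.

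**Working it through.** No sample size, power or event figure depends on this point, so the check is a comparison of texts plus one window calculation.

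**1. Window length.** Day -15 is the day of first study drug, with exposure ascertainment "beginning on the day of the first record of a study drug (palbociclib or letrozole) (Day -15") in Section 7.3.1. The row's window has -16 - (-29) + 1 = 14 days and ends the day before study drug start. If drug start stands in for randomization, this reproduces the trial's two weeks. The window is right; the question is what is looked for inside it.

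**2. The trial criterion, component by component.**

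| Trial component | Named in the real-world rule? | Declared unavailable? | Disclosed? |
|---|---|---|---|
| Major surgery | Yes, cancer-related only | Non-cancer surgery: yes | Yes, validity column |
| Chemotherapy | Through first-line regimen and anti-cancer therapy | Not needed | Not needed |
| Radiotherapy within two weeks | No | No | No |
| Investigational agents | Not by name | Trial-participation dates: yes, in a separate Table 5 row | Yes, in that row |
| Other anti-cancer therapy | Yes, within first-line or (neo)adjuvant therapy | Not needed | Not needed |
| Radiotherapy to a large share of marrow, any time | No | Yes | Yes, validity column |

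Recent radiotherapy is the only component that is not named, not declared unavailable and not disclosed. Section 8 lists design elements that could not be emulated and does not mention it either.

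**3. Does the stated data limitation explain the omission?** The rationale column says that the extent of radiotherapy is unknown. That accounts for the marrow clause. It says nothing about whether receipt or date is unknown, and those are what the two-week clause needs.

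**4. Is there any radiation information in the source?** Table 9 plans a curative-setting radiation variable with the window [Start of data, Day -16]. Some records therefore exist, and the window presumes some dating. The variable does not show that radiotherapy outside the curative setting is captured.

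**5. What happens to a patient with such radiotherapy?** Take a patient irradiated eight days before study drug start, outside both first-line and (neo)adjuvant therapy. She has no earlier first-line regimen, no other anti-cancer therapy in the two named settings and no major cancer surgery, so the rule retains her. The trial criterion would have barred her. In Table 9 the curative-setting radiation variable does not register that treatment.

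**The case against.** The strongest reply is that radiotherapy is an anti-cancer therapy, so the general wording of the row already covers it. The trial criterion itself speaks of radiotherapy and then of other anti-cancer therapy, which supports that reading. It stands in part. Radiotherapy given as (neo)adjuvant treatment can reasonably be read as covered, so a reader who infers that the row drops radiotherapy altogether goes too far. But the row ties the general term to first-line and (neo)adjuvant therapy. Radiotherapy given outside those settings is not covered, and Section 7.8 has two analysts check the implementation against a text that does not tell them to look for it.

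Three further replies have force:

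- The lack of an Appendix C entry proves little alone. The appendix also has none for curative-setting radiation, CYP3A4 inducers or QT-prolonging drugs, all of which the plan uses.
- Table 9 shows capture in the curative setting only, so dated records of other radiotherapy may not exist. This limits what can be applied, but it does not excuse silence: neighbouring rows say when an element cannot be identified.
- The confounding path is partly covered. Table 9 includes metastatic site with a bone-only level, number of sites and performance status.

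The planned CONSORT diagram does not answer the point. It shows who was excluded and why, not who should have been excluded and was kept.

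**Conclusion.** The point holds for radiotherapy given outside first-line and (neo)adjuvant therapy in the two weeks before study drug start. Such patients enter the cohort although the trial barred them, and the plan does not say so. This rests on two assumptions: that study drug start stands in for randomization, and that the general anti-cancer wording is limited to the settings the row attaches to it.

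The size is unknown. The feasibility counts in Section 7.9 (944 and 660) carry no breakdown by radiotherapy and precede the full eligibility criteria, so applying a guessed percentage to them would not be informative. The direction of any effect on the hazard ratio cannot be determined.

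A reader might also infer that the same row wrongly removes women who switch directly from adjuvant endocrine therapy and so thins the subgroup "Most recent therapy (aromatase inhibitor, antiestrogen"). The documents do not support that:

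- The row applies the trial's own two-week bar on other anti-cancer therapy at the correct length. Lifting it would admit women treated inside a window that the trial excluded.
- Nothing in the documents says how often direct switching occurs in routine care.
- Women whose last adjuvant treatment lies more than 14 days before study drug start are not excluded by this row.
- Table 9 assesses earlier aromatase inhibitor or antiestrogen use from the start of data, so the subgroup does not depend on treatment in the last 14 days.

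**What to change.** In the real-world column of this Table 5 row, add any radiotherapy record with the window [Day -29, Day -16], and add a matching radiotherapy list to Appendix C. If radiotherapy outside the curative setting is not captured with dates, apply the exclusion to the records that exist and state in the validity column that patients with other recent radiotherapy may be included. Leave the rest of the row, including the two-week look-back for (neo)adjuvant therapy, as it is.

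The cost is one line in Table 5, one code list and a small loss of sample. The CONSORT diagram already planned can show that loss if radiotherapy is listed as its own reason for exclusion.

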7.4 Variables

7.4.1 Context and rationale for exposures of interest

Operational definitions for the two treatment strategies that will be compared are presented in [Table 6](#). Exposure will be defined based on treatment initiated during the 15-day exposure ascertainment window. While patients in the PALOMA-2 trial received study treatments on the same day, a 15-day window was selected to allow for potential delays in data entry and treatment administration variability that may occur in routine practice. In a feasibility assessment of 944 patients in the data source who initiated both letrozole and palbociclib as first-line therapy, 93.3% started both medications within 15 days. A shorter exposure window may be too restrictive and result in few eligible patients, while longer time periods may result in treatment patterns in the study population that are vastly different from the trial. As discussed above, patients who experience a censoring event or death during the exposure ascertainment window will be excluded from the study to align the start of follow-up for both exposure groups.

Table 6. Operational Definitions of Exposures

Group name(s)	Details	Washout window	Assessment Window	Incident with respect to...	Source of algorithm	Validity concerns and how they will be addressed
Exposed	Patients initiating treatment with palbociclib and letrozole within 15 days of one another, in the metastatic setting	N/A, treatment in first-line metastatic setting	[Metastatic diagnosis date, Day -1]	Metastatic Diagnosis	Curated regimen definition; clinical experts	Real-world exposure group definitions allow for more flexibility in treatment timing than in the trial. The potential impact of this on results will be explored through a sensitivity analysis shortening the duration of the exposure ascertainment window (Table 11).
Comparator	Patients initiating treatment with letrozole with no evidence of palbociclib treatment within 15 days, in the metastatic setting	N/A, treatment in first-line metastatic setting	[Metastatic diagnosis date, Day -1]	Metastatic Diagnosis	Curated regimen definition; clinical experts	

N/A = not applicable

7.4.2 Context and rationale for outcome of interest

The operational definition of the outcome of interest, rwPFS, is presented in [Table 7](#). This outcome corresponds to the primary outcome of the PALOMA-2 trial.

Table 7. Operational Definitions of Outcome

Outcome name	Details	Primary outcome	Type of outcome	Washout window	Source of algorithm	Validity concerns and how they will be addressed
rwPFS	Time from Day 0 to disease progression or death	Yes	Time-to-event	N/A	Progression events are curated in the data. All tumor progression events after initial cancer diagnosis are captured.	Real-world progression is not evaluated at fixed intervals as was done in the trial. The frequency and timing of real-world progression assessment results by exposure group will be reported to contextualize study findings.

N/A = not applicable

7.4.3 Context and rationale for follow-up

Follow-up will begin on Day 0, and will continue until the earliest of:

1. Date of documented progression or death ([Table 7](#));
2. Initiation of any new anti-cancer therapy;
3. The administrative end of the study period (Day 1004, or 33 months, of follow-up), to align with the maximum follow-up time at which PFS was evaluated in the PALOMA-2 trial;
4. End of the data (July 20, 2023);
5. Loss to follow-up: The last date of curated EHR activity prior to a period of >90 days without curated EHR activity and without death.

Operational definitions for the study censoring criteria are presented in [Table 8](#). These censoring criteria correspond to those applied in the PALOMA-2 RCT where applicable.

Table 8. Operational Definitions of Censoring Criteria

Trial Criterion	Real-world operationalization	Rationale for real-world operationalization (where applicable)	Validity concerns and how they will be addressed (where applicable)
Initiation of a new anti-cancer treatment	Treatment with any new anti-cancer therapy.	N/A	N/A

Trial Criterion	Real-world operationalization	Rationale for real-world operationalization (where applicable)	Validity concerns and how they will be addressed (where applicable)
End of study	Administrative end of study (Day 1004, or 33 months) or July 20, 2023.	Align with maximum time in PALOMA-2 or end of available data in real-world data source.	N/A
Withdrawal of consent	This criterion is not relevant in a real-world clinical setting.	N/A	N/A
Loss to follow-up	A period of >90 days without curated EHR activity and without death.	Curated activity in the real-world data source indicates points at which progression can be recorded. Metastatic breast cancer patients likely have contact with the healthcare system at least every 90 days for lab work, prescription refills, outpatient visits, or scans. Periods greater than 90 days may indicate loss to follow-up during which censoring or outcome events cannot be captured.	Patients who use the health care system less frequently will be censored. A sensitivity analysis will be conducted expanding the period without curated activity to >180 days (Table II).
≥2 missed disease assessments	This criterion will not be operationalized.	Real-world progression is not evaluated at fixed intervals as was done in the trial. Patients with gaps in activity of greater than 90 days will be censored under the loss to follow-up definition.	The frequency of real-world progression assessments will be reported to contextualize study findings.

N/A = not applicable

7.4.4 Context and rationale for covariates (confounding variables and effect modifiers, e.g., risk factors, comorbidities, comedICATIONS)

Operational definitions for the study covariates are presented in [Table 9](#). Covariates were chosen based on the primary trial publication and the research team’s substantive knowledge of potential confounders. For time-varying characteristics, the value closest in time prior to study drug initiation will be used.

Table 9. Operational Definitions of Covariates

Characteristic	Details/Levels ^a	Type of variable	Assessment window
Patient Demographic Characteristics			
Age	Age at study drug initiation 18 to <65 yrs, ≥65 yrs	Continuous, Categorical	[Day -15]
Race	American Indian or Alaska Native, Asian, Native Hawaiian or other Pacific Islander, Black or African American, White, other or unknown race	Categorical	[Start of data, Day -15]
Ethnicity	Hispanic or Latino, not Hispanic or Latino, unknown	Categorical	[Start of data, Day -15]
Region	Northeast, south, midwest, west, missing	Categorical	[Start of data, Day -15]
Clinical Characteristics			
Oncology clinic site type	Academic, community, missing	Categorical	[Start of data, Day -15]
Performance status	ECOG performance status 0, 1, 2, or Karnofsky performance status 50, 60, 70, 80, 90, 100, or missing.	Categorical	[Day -105, Day -15]
Smoking status at initial diagnosis	Current smoker, former smoker, non-smoker, missing	Categorical	[Start of data, Initial diagnosis date]
Number of outpatient visits in past year	N/A	Continuous	[Day -380, Day -15]
Disease Characteristics and Treatment History			
Year of study treatment initiation	N/A	Categorical	[Day -15]
Prior therapy	Aromatase inhibitor, antiestrogen	Dichotomous	[Start of data, Day -15]
Disease stage at initial diagnosis	Disease stage I-IV	Categorical	[Initial diagnosis date - 30, Initial diagnosis date + 90]

Characteristic	Details/Levels ^a	Type of variable	Assessment window
Time between metastatic diagnosis and treatment initiation	N/A	Continuous	[Metastatic diagnosis date, Day -15]
Time interval between initial diagnosis and metastatic diagnosis (approximate disease-free interval)	N/A	Continuous	[Initial diagnosis date, Metastatic diagnosis date]
Prior neoadjuvant or adjuvant chemotherapy	Yes, no	Dichotomous	[Start of data, Day -16]
Prior neoadjuvant or adjuvant hormone therapy	Yes, no	Dichotomous	[Start of data, Day -16]
Surgery in the curative setting	Yes, no	Dichotomous	[Start of data, Day -16]
Radiation in the curative setting	Yes, no	Dichotomous	[Start of data, Day -16]
Recurrence type	Recurrent, de novo metastatic, missing	Categorical	[Initial diagnosis date - 30, Initial diagnosis date + 90]
Metastatic disease site	Visceral (lung, including pleura, liver), non-visceral (all others), bone only	Categorical	[Start of data, Day -15]
Number of metastatic disease sites	1, 2, ≥3	Continuous, Categorical	[Start of data, Day -15]

N/A = not applicable

^a See [Appendix C](#) for code list.

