Documentation of histologically or cytologically confirmed diagnosis of ER+ breast cancer based on local laboratory results.	ER biomarker test with a result interpretation of 'Positive.' For patients with multiple ESR1 tests, the entry closest in time to study drug initiation will be used.	[Start of data, Day -15]	N/A	N/A
Previously untreated with any systemic anti-cancer therapy for their locoregionally recurrent or metastatic ER+ disease	No first-line regimen for metastatic disease prior to study drug initiation.	[Metastatic diagnosis date, Day -16]	N/A	N/A

Trial Criterion	Real-world operationalization ^a	Assessment window	Rationale for real-world operationalization (where applicable)	Validity concerns and how they will be addressed (where applicable)
Postmenopausal women, defined as women with prior bilateral surgical oophorectomy or medically confirmed post-menopausal status	Surgery indicative of bilateral surgical oophorectomy or recorded post-menopausal status. Age >50 years if both of the above are missing.	[Start of data, Day -15]	Age >50 years will be used as a proxy for post-menopausal status for patients with missing data. This reflects the average age of menopause for females in the U.S. ¹³	Patients >50 years of age but who are not postmenopausal and who would have been ineligible for the trial may be included. This may affect comparability between the study and trial populations.
Measurable disease as defined per RECIST v.1.1	This criterion cannot be operationalized.	N/A	RECIST assessments are not performed in routine oncology care.	Patients with non-measurable disease who would have been ineligible for the trial may be included. This may result in longer estimates of rwPFS than were observed in the trial due to difficulties in objectively measuring progression for these patients.

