
Known active, uncontrolled, or symptomatic central nervous system metastases, carcinomatous meningitis, or leptomeningeal disease as indicated by clinical symptoms, cerebral edema, and/or progressive growth. Patients with a history of central nervous system (CNS) metastases or cord compression are eligible if they have been definitively treated with local therapy (e.g., radiotherapy, stereotactic surgery) and are clinically stable off anticonvulsants and steroids for at least 4 weeks before randomization
	
Diagnosis of brain, CNS, and/or spinal cord metastases.
	
[Start of data, Day -15]
	
Active, uncontrolled, or symptomatic CNS metastases and diagnoses of carcinomatous meningitis and leptomeningeal disease cannot be identified in the data source. Definitive treatment with local therapy and clinical stability without anticonvulsants and steroids cannot be identified in the data source.
	
Patients with a history of CNS metastases who would have been eligible for the trial (those who received definitive treatment and were clinically stable at study drug initiation) may be excluded. This may affect comparability between the study and trial populations.

Prior neoadjuvant or adjuvant treatment with a non-steroidal aromatase inhibitor (i.e., anastrozole or letrozole) with disease recurrence while on or within 12 months of completing treatment
	
Neoadjuvant or adjuvant treatment with anastrozole or letrozole with time between the last date of neoadjuvant or adjuvant therapy and metastatic diagnosis \leq12 months.
	
[Metastatic diagnosis date -365 days, Metastatic diagnosis date - 1 day]
	
N/A
	
N/A

Prior treatment with any cyclin-dependent kinase 4/6 (CDK4/6) inhibitor
	
Treatment with ribociclib, abemaciclib, or palbociclib.
	
[Start of data, Day -16]
	
N/A
	
N/A

Trial Criterion	Real-world operationalization ^o	Assessment window	Rationale for real-world operationalization (where applicable)	Validity concerns and how they will be addressed (where applicable)

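### The Prior therapy covariate window in Table 9 includes the study-drug start day, so study letrozole counts as prior aromatase inhibitor use

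*Combined protocol and SAP*

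**What the plan says.** Table 9 defines Prior therapy as a dichotomous variable with levels "Aromatase inhibitor, antiestrogen", assessed from the start of data to Day -15 inclusive. The text above the table sets a general rule: "For time-varying characteristics, the value closest in time prior to study drug initiation will be used".

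Section 7.3.1 anchors the day count. The 15-day exposure window opens "beginning on the day of the first record of a study drug (palbociclib or letrozole) (Day -15") and closes on Day -1. Table 5 identifies letrozole as a "non-steroidal aromatase inhibitor (i.e., anastrozole or letrozole").

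Other treatment-history items stop one day earlier, on Day -16. Examples are "No first-line regimen for metastatic disease prior to study drug initiation" in Table 4, "Treatment with ribociclib, abemaciclib, or palbociclib" in Table 5, and "Prior neoadjuvant or adjuvant hormone therapy" in Table 9.

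Under Table 10, all Table 9 variables are candidates for the propensity-score model, and the final form is settled at analysis. Table 10 also lists a subgroup by most recent therapy, using the same two drug classes.

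**The concern.** A treatment-history covariate should describe what happened before the study drug. Here the study drug belongs to one of the covariate's own levels, and the window includes the day it starts. The row's name and the rule above the table point to history only; the window cell does not. An analyst who follows the cell gets a variable that carries no history for comparators. For exposed patients it partly records which study drug was entered first.

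The propensity score would then not adjust for prior AI versus prior antiestrogen. If the row were dropped as uninformative, the same information would be lost. Table 9 could also contradict itself for one patient: a comparator with no (neo)adjuvant endocrine therapy would be *no* for prior hormone therapy and *yes* for prior AI.

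A side issue is the coding. If the two drug classes are the two levels of a dichotomous variable, a patient who received neither has no level.

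**Working it through.** **Day count.** Day -15 to Day -1 is 15 days, so Day -15 is the start day and Day -16 is the last day before it.

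**End days of the anti-cancer treatment-history windows tied to study-drug start**

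| Table | Item | Ends |
|---|---|---|
| 4 | Previously untreated for metastatic disease | Day -16 |
| 5 | Prior CDK4/6 inhibitor | Day -16 |
| 5 | Recent surgery or anti-cancer therapy | Day -16 |
| 9 | (Neo)adjuvant chemotherapy | Day -16 |
| 9 | (Neo)adjuvant hormone therapy | Day -16 |
| 9 | Surgery in the curative setting | Day -16 |
| 9 | Radiation in the curative setting | Day -16 |
| 9 | **Prior therapy (AI, antiestrogen)** | **Day -15** |

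That is 1 + 2 + 4 = 7 windows ending on Day -16, against one ending on Day -15. The Table 3 washout also ends on Day -16. Other rows end on Day -15 (race, performance status, metastatic sites), but a study-drug record cannot set those values. Appendix C has no Prior therapy entry that would remove study letrozole.

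**Coding that results.** A comparator has no palbociclib in the exposure window, so the Day -15 drug is letrozole and 100% of comparators are coded AI = yes. An exposed patient is coded AI = no only if palbociclib was recorded first and there was no earlier AI. The documents do not give the share of such patients.

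**Would the balance check notice?** This illustration reads the row as AI yes/no.

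- Inputs: of 944 feasibility patients who started both drugs, 93.3% did so within 15 days (Section 7.4.1), so 0.933 × 944 = 880.8, about 881 exposed. There are 660 comparators (Section 7.9). The total is 1,541, before all criteria are applied.
- Let k exposed patients and no comparators be AI = no. That level separates completely: fitted propensity 1, weight 1. The AI = yes exposed patients weight up to about 1541 − k.
- The weighted share of AI = no is q = k/1541 in the exposed and 0 in comparators. The absolute standardized difference (ASD) is q / √(q(1−q)/2) = √(2q/(1−q)).

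| k | ASD | Against the 0.1 limit (Section 7.5.1) |
|---|---|---|
| 0 | 0 | passes |
| 7 (0.8%) | 0.096 | passes |
| 8 (0.9%) | 0.102 | fails |
| 44 (assumed 5%) | 0.242 | fails |

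A simulation with a multivariable propensity score (eight standard-normal covariates) gave mean ASDs of 0.095–0.096, 0.102 and 0.242 for k = 7, 8 and 44. So the check passes silently only if almost no exposed patient is AI = no. Otherwise it flags a level that weighting cannot balance, because no comparator is in it.

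**Possible effect on the hazard ratio.** Take prior AI use as wholly unadjusted, with prevalence p₀ = 0.20 in one group and p₁ in the other, and a prior-AI effect on progression of h. All three are assumptions. Bias factor = (1 + p₁(h−1)) / (1 + p₀(h−1)).

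- p₁ = 0.25, h = 1.2: 1.05/1.04 = 1.010
- p₁ = 0.30, h = 1.5: 1.15/1.10 = 1.045
- p₁ = 0.35, h = 1.5: 1.175/1.10 = 1.068

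Applied to the trial's 0.58 (Table 13), the largest factor gives 0.58 × 1.068 = 0.62 or 0.58 / 1.068 = 0.54.

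**The case against.** The strongest reply is that the row's name and the Section 7.4.4 rule already exclude the study drug, so a sensible analyst would ignore Day -15. That shows the intent but does not protect the row. The protocol describes performance status (Table 4) and CYP3A4/QT drugs (Table 5) as assessed before study-drug start and still ends those windows on Day -15, so its use of *prior* does not reliably exclude that day. If Day -15 counts, the closest-in-time rule selects study letrozole even over earlier tamoxifen.

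A second reply is that the error would be caught. Section 7.5.1 plans a table of comparators before and after 2015, where a 100% prior-AI rate would be visible, and Section 7.8 has two analysts check every variable. This has weight: silent failure is not certain. But the Section 7.8 check is against the protocol, and code that follows the cell agrees with the protocol.

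Third, eligibility limits the confounding. Table 5 removes patients whose anastrozole or letrozole ended within 12 months before metastatic diagnosis, and Table 4 removes earlier first-line regimens. Genuine prior AI use is therefore mostly curative-setting therapy, which overlaps the hormone-therapy row. This stands, and it is a reason to rate the point minor.

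Fourth, the figures rest on assumptions. This also stands. The bias factor treats prior AI use as wholly unadjusted, whereas only the drug-class split is lost. The ASD crossing point depends on counts: if all 63 late starters (944 − 881) became comparators, N would be 1,604 and k = 8 would give 0.1001. Finally, *dichotomous* could mean one yes/no flag per class, so the missing-level point is an ambiguity, and the main finding does not depend on it.

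**Conclusion.** The concern holds as a minor specification error. The stated window codes the study drug as prior therapy, and it conflicts with the row's own name and with every comparable window. Confidence in that textual finding is high.

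The consequence is limited to losing the AI-versus-antiestrogen distinction from the adjustment, and only if the cell is applied literally. The documents do not show a biased hazard ratio. The 0.54 to 0.62 range around 0.58 rests entirely on assumed prevalences and effects, has unknown direction, and takes no credit for the hormone-therapy row or other correlated covariates. The ASD figures are likewise illustrative, because neither the palbociclib-first share nor the final propensity model is known.

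**What to change.** In Table 9, end the Prior therapy window on Day -16. Define AI and antiestrogen as two separate yes/no indicators, or keep one variable and add a level for patients with neither. If the most-recent-therapy subgroup in Table 10 is built from this variable, give it the same Day -16 window; otherwise its antiestrogen level would hold essentially no comparators.

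The cost is one table cell and one level definition. No new data are needed, and the Table 13 sample sizes do not change.
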